6.4.5 Prior and concomitant therapy

A prior and concomitant therapy is any drug or substance administered from the screening visit until the EOS visit. The investigator must instruct patients and/or legal representatives to notify the study site about any new medications taken after the patient has been screened for the study. All medications, non-drug therapies (including physical therapy and blood transfusions) administered after the patient was enrolled must be recorded in the eCRF. Information about medication name, indication, dose, unit, frequency, route date and time is to be recorded for each medication.

Any conventional treatment for pHLH (including but not limited to plasmapheresis, HSCT) must be recorded, regardless of when it has been received.

No other medicinal product under investigation may be used concomitantly with the IMP in this study.

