6.4.5.2.4 Other treatments

Analgesic treatment, transfusion of blood products, electrolyte and glucose infusions, antibiotics, antifungal and anti-viral treatment, and general supportive care (e.g. gastro-protective agents) are allowed. The use of any prescription or over-the-counter medication, including herbal and homeopathic preparations with the exception of multi-vitamins, needs to be notified to the Investigator.

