6.5.4 Efficacy endpoints assessments

6.5.4.1 Overall Response

Overall Response is defined as achievement of either Complete or Partial Response or HLH Improvement, at EOT or week 8 (whichever occurs earlier).

Complete response, partial response and HLH improvement and time to first response will be assessed after the database lock via a programmed algorithm, based on the Table 5 below.

Table 5 Definition of response

Overall Response	
Complete Response	Complete Response is adjudicated if:

	
 - No fever = body temperature <37.5°C - Normal spleen size - No cytopenia = Absolute Neutrophil Counts $\geq 1.0 \times 10^9/L$ and platelet count $\geq 100 \times 10^9/L$ [absence of G-CSF and transfusion support must be documented for at least 4 days to report no cytopenia] - No hyperferritinemia = serum level is <2000 µg/L - No evidence of coagulopathy, i.e., normal D-Dimer and/or normal (>150 mg/dL) fibrinogen levels - No neurological and CSF abnormalities attributed to HLH - No sustained worsening of sCD25 (as indicated by at least two consecutive measurements that are > 2-fold higher than baseline)
Partial Response	
Partial Response is adjudicated if:
 
 - At least 3 of the HLH clinical and laboratory abnormalities (including CNS abnormalities) meet the above-mentioned criteria for "Complete Response" - In the case of "reactivated patients" who enter the study with 3 abnormal HLH features, Partial Response is adjudicated if at least 2 parameters normalize - In case of reactivated patients who enter the study with 2 abnormal HLH clinical and laboratory parameters only, Partial Response is adjudicated if one of the 2 parameters normalizes - There is no progression of other aspects of HLH disease pathology
HLH improvement	
 - Improvement (>50% change from baseline or normalization) of at least 3 HLH clinical and laboratory abnormalities (including CNS abnormalities). - In the case of "reactivated patients" who enter the study with only 2 abnormal HLH features, a change from baseline greater than 50% for both will define HLH as improved.

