## **6.8.2. Secondary Analysis Supporting Secondary Objectives**

### Overall Response

Achievement of response will be assessed after the database lock via a programmed algorithm. The derivation of the Overall Response is detailed below.

Overall Response		
Response	Definition	Additional Clarifications
Complete Response	Complete Response is adjudicated if: 
 
- No fever = body temperature <37.5°C
 
- Normal spleen size
 
- No cytopenia = Absolute Neutrophil Counts <math>\geq 1.0 \times 10^9/L</math> and platelet count <math>\geq 100 \times 10^9/L</math> [absence of G-CSF and transfusion support must be documented for at least 4 days to report no cytopenia]
 
- No hyperferritinemia = serum ferritin level is <2000 <math>\mu g/L</math>
 
- No evidence of coagulopathy, i.e., normal D-Dimer and/or normal (>150 mg/dL) fibrinogen levels
 
- No neurological and CSF abnormalities attributed to HLH
 
- No sustained worsening of sCD25 (as indicated by at least two consecutive measurements that are > 2-fold higher than baseline)
 
	
 
- All HLH parameters that were abnormal at baseline must be normalized
 
- No AEs relating to organ failure
 
- All other parameters that were normal at baseline must still meet the definition of normalized
 
- Normal spleen size confirmed by abdominal ultrasound (US) whenever possible based on the splenomegaly not present; if US not performed physical examination will be used
 
- Normal D-Dimer levels are <math>\leq 500 \mu g/L</math>
 
- No neurological abnormalities attributed to HLH = “normal” neurological assessment by investigator in the neurological examination page (without findings in brain imaging (Brain MRI/Brain CT/cranial ultrasound) or AEs indicative of “CNS involvement”
 
- No CSF abnormalities = no AE indicative of “CSF abnormalities”
 

Partial Response	Partial Response is adjudicated if: 
 
- At least 3 of the HLH clinical and laboratory abnormalities (including CNS abnormalities) meet
 
	If a patient is not considered as “reactivated” or a patient is considered “reactivated” with 4 or more abnormal HLH features upon entry to the study and

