	
the above mentioned criteria for “Complete Response”
 
 
- In the case of “reactivated patients” who enter the study with 3 abnormal HLH features, Partial Response is adjudicated if at least 2 parameters normalize
 
- In case of reactivated patients who enter the study with 2 abnormal HLH clinical and laboratory parameters only, Partial Response is adjudicated if one of the 2 parameters normalizes
 
- There is no progression of other aspects of HLH disease pathology
 
	
at least 3 of the HLH clinical and laboratory abnormalities (including CNS abnormalities) meet the above-mentioned criteria for “Complete Response” Partial Response is adjudicated.
 
For all patients: no progression of other aspects of HLH disease pathology is assessed by absence of AEs indicating organ failure including no worsening of sCD25 levels.

HLH improvement	
HLH Improvement is adjudicated if:
 
 
- Improvement (>50% change from baseline or normalization) of at least 3 HLH clinical and laboratory abnormalities (including CNS abnormalities).
 
- In the case of “reactivated patients” who enter the study with only 2 abnormal HLH features, a change from baseline greater than 50% for both will define HLH as improved.
 
	
Definition of 50% improvement from baseline:
 
 
- Spleen size decreased by 50%, as recorded in cm from costal margin at physical examination.
 
- Absolute Neutrophil Count increased by 50%, if G-CSF has not been administered in the previous 4 days and Platelet count increased by 50%, if no platelet transfusion has been administered in the previous 4 days
 
- Ferritin decreased by 50%
 
- Fibrinogen increased by 50% or D-Dimer decreased by 50%
 
 
Normalization of CNS abnormalities = normal neurological assessment by investigator without findings in brain imaging (Brain MRI/Brain CT/cranial ultrasound), CSF analysis or AEs indicative of “CNS involvement” or “CSF abnormalities”

No Response	
If a subject does not meet the criteria for at least HLH improvement, response is categorized as “No Response”
	

Abbreviations: CNS, central nervous system; CSF, cerebrospinal fluid; G-CSF, granulocyte-colony-stimulating factor; HLH, hemophagocytic lymphohistiocytosis
		

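### Fibrinogen alone can satisfy the coagulopathy item of Overall Response with no condition on recent plasma or fibrinogen replacement, although the same table requires support-free days for blood counts

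*SAP*

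**What the plan says.** - **Normalisation.** Protocol Table 5 (section 6.5.4.1) has "No evidence of coagulopathy, i.e., normal D-Dimer and/or normal (>150 mg/dL) fibrinogen levels". SAP 6.8.2 and 6.12 repeat it and set normal D-dimer at 500 µg/L or below. Partial Response counts items by these criteria, and HLH Improvement accepts them as one of its two routes.
- **50% improvement.** SAP 6.8.2 and 6.12: "Fibrinogen increased by 50% or D-Dimer decreased by 50" (per cent).
- **Support rules in the same table.** The cytopenia item carries "absence of G-CSF and transfusion support must be documented for at least 4 days to report no cytopenia". In the 50% rules, neutrophils count only "if G-CSF has not been administered in the previous 4 days", and platelets have a parallel 4-day clause for platelet transfusion.
- **Supportive care.** Protocol 6.4.5.2.4 allows "transfusion of blood products, electrolyte and glucose infusions", and 6.4.5.3.4 again allows blood products. Neither section limits the type of product.
- **Recording.** Protocol 6.4.5: "non-drug therapies (including physical therapy and blood transfusions) administered after the patient was enrolled must be recorded in the eCRF". Medications are recorded too.
- **Derivation.** SAP 6.8.2 derives response by program after database lock, under a treatment policy strategy. SAP 6.1 lets the data review meeting exclude single data points but gives no criterion for fibrinogen.

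**The concern.** The table accepts that a blood count under support is not evidence of response. It does not apply that principle to fibrinogen, although hypofibrinogenemia is listed among the typical features of HLH (protocol 4.1) and is part of a diagnostic criterion (protocol 6.3.1). Because fibrinogen alone is enough, an abnormal D-dimer does not block the item. A patient whose fibrinogen was raised by a transfused product can be credited with one resolved HLH abnormality. At stake are Overall Response, time to first response and cumulative duration of response, all from the same algorithm.

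**Working it through.** **1. Clauses side by side (SAP 6.8.2)**

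| Item | Normalised | 50% improved | Support-free condition |
|---|---|---|---|
| Neutrophils | at least 1.0 × 10⁹/L | up 50% | 4 days |
| Platelets | at least 100 × 10⁹/L | up 50% | 4 days |
| Coagulopathy | D-dimer normal and/or fibrinogen above 150 mg/dL | fibrinogen up 50% or D-dimer down 50% | none |

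**2. Fibrinogen values through the rule.** The values are illustrative assumptions. Change = (post − baseline) / baseline.
- 100 to 151 mg/dL: 51/100 = 51.0%, and above 150. Both routes are met.
- 140 to 151 mg/dL: 11/140 = 7.9%, but above 150. Normalised.
- 90 to 160 mg/dL: 70/90 = 77.8%, and above 150. Both routes are met.
- 90 to 135 mg/dL: 45/90 = exactly 50.0%. This fails the definition column of SAP 6.8.2, which needs more than 50%, so I do not rely on it.

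In no case does the rule ask what caused the rise or require D-dimer to move.

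**3. Weight of one item**
- Partial Response and HLH Improvement generally need 3 items, so coagulopathy is 1/3 of the requirement.
- A reactivated patient with 3 abnormal features needs 2 for Partial Response (1/2).
- A reactivated patient with 2 abnormal features needs 1 for Partial Response (the whole feature requirement).
- Partial Response also needs no organ-failure AE and no sCD25 worsening.
- The definition column of SAP 6.12 opens the two- and three-feature branches to any patient, which widens the exposure.

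**4. Size per reclassified patient.** Shift = 100/N: 100/10 = 10.0 points; 100/18 = 5.6 points. Clopper-Pearson intervals are the SAP's method. As a check, 27/45 gives 44.3% to 74.3%, matching protocol 4.1.1.3.2. Near 60% (an assumed rate):
- 6/10 = 60.0% (26.2 to 87.8) against 7/10 = 70.0% (34.8 to 93.3)
- 11/18 = 61.1% (35.7 to 82.7) against 12/18 = 66.7% (41.0 to 86.7)

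**5. Time endpoints.** Overall Response is read at one visit, but time to first response is open at every treatment visit, and these are 3 to 4 days apart. One qualifying visit fixes the event date. Cumulative duration assumes a response holds until the next visit, so one such visit adds 3 to 4 days for that patient. It also brings in a patient who would otherwise be excluded as never responding, and that patient contributes a short value.

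**6. Direction.** Baseline is the last value before first dose (SAP 6.1), also with no replacement condition. Suppose replacement lifts a true 90 to a baseline of 140. From 90 the easier route is the 50% rule, above 90 × 1.5 = 135. From 140 it is normalisation, above 150, because 140 × 1.5 = 210 is higher. If baseline is lifted above 150 and the same rule is applied there, the item is not abnormal and cannot count towards response.

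**The case against.** - **Inflation is not shown.** This stands. A reader might infer that the response rate is inflated by supportive care. The documents give no frequency of replacement and do not name plasma, cryoprecipitate or fibrinogen concentrate. The first two fall under blood products; the third is neither named nor prohibited. A replaced baseline can pull the other way, and a patient can receive replacement and improve at the same time.
- **Complete Response may already be covered.** This partly stands. If transfusion support in the cytopenia item includes plasma products, a recent recipient cannot be a Complete Responder and also loses the cytopenia item towards Partial Response. But the wording does not settle this, it does not condition the coagulopathy item, and the 50% rules exclude only G-CSF and platelet transfusion. HLH Improvement stays open.
- **The either/or logic is deliberate.** This stands. Protocol Table 2 requires both D-dimer and fibrinogen to be unfavourable before coagulopathy supports a dose increase, so calling it absent when one is normal is consistent. The gap is the missing replacement condition.
- **Treatment policy and listings handle it.** This does not stand as a remedy. Treatment policy is the reason a post-replacement value would count. Per-subject listings would let a reader look for a case among at most 18 patients, but exclusion at data review is discretionary and has no stated rule.
- **The endpoint is secondary and descriptive.** This is true and limits the weight. The primary endpoint is safety, and no hypothesis is tested.

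**Conclusion.** The gap is real. The coagulopathy item can be met by fibrinogen alone with no condition on recent replacement, in a table that applies a 4-day condition to neutrophils and platelets. A post-replacement value can turn No Response into Partial Response or HLH Improvement, bring the first response forward and lengthen a patient's cumulative response. Each affected patient moves Overall Response by 10.0 points (n = 10) to 5.6 points (n = 18).

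Three limits apply. The number of affected patients is unknown and the net direction is not established. One item usually does not make a responder; the exception is the two-feature case. Complete Response may be protected indirectly. The example fibrinogen values are assumptions that show how the rule works, not how often it matters. A supplementary analysis is proportionate to this.

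**What to change.** Pre-specify in SAP 6.12 a supplementary analysis of Overall Response, time to first response and cumulative duration of response with this rule: a post-baseline fibrinogen value obtained within 4 days after a recorded plasma, cryoprecipitate or fibrinogen product does not count as normalised or improved, and the item is judged on D-dimer alone. The 4 days is the table's own window for blood counts; nothing in the documents supports it for fibrinogen specifically, so the sponsor should confirm it. Flag patients whose baseline fibrinogen followed replacement. State whether transfusion support in the cytopenia item includes plasma products.

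If the sponsor would rather change the main definition, record it in SAP section 9 and align protocol Table 5. Otherwise the two documents would disagree.

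Cost: SAP wording and programming, with no new data field planned and no restriction on treatment. D-dimer is in the coagulation panel at every treatment visit, so the item normally stays assessable. Some visits lose the fibrinogen route, so the supplementary response rate may be slightly lower. SAP 6.6 lists only name, dates, indication and ongoing status for non-drug therapy, so product type must be identifiable from the recorded name. This should be checked before database lock.

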**Figure 1. Overview of the study design**

SCREENING	TREATMENT					FOLLOW-UP					
Day -14 to Visit 1	Visit 1 (SD 0)	Visit 2 (SD 3-4 and onwards) every 3-4 days	W8 Primary assessment timepoint if treatment continues	W9-onwards until start of conditioning for HSCT	EOT (3±1 day after last infusion)  Primary assessment timepoint if treatment stopped before week 8	Pre-HSCT		Post HSCT			
	Initial dose	Subsequent doses				Pre-conditioning	W 1/2/3	D 30	D 60	D 100	M6

Abbreviations SD, study day; EOT, end of treatment; HSCT, hematopoietic stem cell transplant; W, week; D, day after HSCT; M, month; EOS, end of study

The patient will enter screening after informed consent is obtained and will undergo screening assessments to confirm eligibility. Duration of the screening period will be kept as short as possible and should not exceed 2 weeks.

First emapalumab infusion, at a dose of 1 mg/kg, marks the start of the treatment period. The treatment period is foreseen to continue until start of conditioning for HSCT, if deemed indicated for this patient. Infusions will take place twice weekly, at a dose determined by the Investigator for each infusion. Emapalumab will be administered on the background of dexamethasone, which can be tapered or increased as needed. No wash-out is required prior to conditioning for HSCT. Last visit of the treatment period is the end of treatment, which occurs 3 days after the last infusion of emapalumab. Assessment of efficacy objectives occurs at end of treatment. After the start of conditioning for HSCT (or treatment completion, if HSCT is not deemed indicated), the patient proceeds to follow-up period. Follow-up visits are planned in relation to the date of the HSCT, or last emapalumab infusion (if HSCT is not deemed indicated). Duration of the follow-up is one year after HSCT, or after the last emapalumab infusion. The end of study visit (EOS) for each patient will occur at the latest 18 months from first dose of emapalumab.

Patient will be considered screened after informed consent is obtained.

For further details on the schedule of events for treatment period and follow-up period, please refer to Table 3 and Table 4 in study protocol.

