	
Secondary Endpoint 4:          Treatment-emergent vital sign abnormalities
	
Estimand 1.4          Target population: All patients received at least one infusion of IMP          Treatment: Refer to Section 6.4 in study protocol          Endpoints: Refer to the left column          Strategies for addressing intercurrent events:          The treatment policy strategy will be applied for the estimand          Population-level summary:          Incidence of treatment-emergent vital sign abnormalities (refer to Section 6.8)

Secondary Objective:          To collect efficacy data on emapalumab in treatment-experienced Chinese pHLH patients
	
Secondary Endpoint 1:          Overall Response, i.e., achievement of either Complete or Partial Response or HLH Improvement, at EOT or Week 8 (whichever occurs earlier)
	
Estimand 2.1          Target population: All patients received at least one infusion of IMP          Treatment: Refer to Section 6.4 in study protocol          Endpoints: Refer to the left column          Strategies for addressing intercurrent events:          The treatment policy strategy will be applied for the estimand          Population-level summary:          The number and percentage of patients achieving overall response and each component of overall response at EOT or week 8 (whichever occurs earlier)

	
Secondary Endpoint 2:          Time to first Overall Response, i.e., time from the date of first dose of
	
Estimand 2.2          Target population: All patients received at least one infusion of IMP

[figure not shown]
	
emapalumab to the first achievement of response (Complete or Partial Response or HLH Improvement)
	
Treatment: Refer to Section 6.4 in study protocol          Endpoints: Refer to the left column          Strategies for addressing intercurrent events:          The treatment policy strategy will be applied for the estimand          Population-level summary:          Time to first response prior to HSCT will be estimated using Kaplan-Meier method

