### **6.3. Subject Disposition**

The number of subjects will be calculated for all screened subjects. Subject will be considered screened after informed consent/assent is obtained.

Based on all screened subjects, the number and percentage of screen failures will be presented, as the main reason for screen failures will be tabulated. Screen failures will be listed.

Based on all screened subjects, the number and percentage of treated subjects who received the first dose of emapalumab will be presented.

Based on all treated subjects (subjects who received the first dose of emapalumab), the number and percentage of subjects who completed the treatment period prior to HSCT and those withdrawn from the treatment will be presented. The reason for withdrawal will be tabulated. Subjects withdrawn from the treatment period will also be listed.

Based on all subjects who completed the treatment period prior to HSCT, the number and percentage of subjects receiving HSCT and those who did not following the end of treatment will be presented. The reason for not receiving HSCT will also be tabulated.

Based on all subjects who completed the treatment period, the number and percentage of subjects who proceeded into the follow-up period and those who did not will be presented.

Based on all subjects who proceeded into the follow-up period, the number and percentage of subjects who completed the follow-up period and those who did not will be presented. The reason for withdrawal will also be tabulated. Subjects withdrawn from the follow-up period will also be listed.

Based on all screened subjects, the number and percentage of subjects included in the all treated analysis set will be calculated and summarized. A listing will be provided for subjects excluded from the analysis set with the reason of exclusion presented.

Based on all screened subjects excluding screen failures, important protocol deviation will be tabulated by protocol deviation category. Listings will be provided for all protocol deviations.

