 AE indicating organ failures will be pre-specified according to [Appendix 1](#).

 AE indicative of CNS involvement/CSF abnormalities will be pre-specified according to [Appendix 2](#).

The treatment policy strategy will be applied. The achievement of response based on the above definition at EOT or week 8 will be estimated as described below regardless of any potential intercurrent events.

Subjects who failed to meet the definition for above categories (Complete Response, Partial Response or HLH Improvement) will be considered as No Response. The number and percentage of patients achieving Overall Response at EOT or week 8 (whichever occurs earlier), i.e., Complete Response or Partial Response or HLH improvement, as well as No Response will be provided. In addition, 95% confidence interval will be estimated using Clopper-Pearson exact method for the percentages of subjects achieving each Overall Response category. Subjects’ response status and assessments corresponding to each response criterion will be listed.

For subjects that did not withdraw treatment before week 8, observed data from the visit closest to 56 days (8 weeks) after first infusion will be used in the analysis. If there are more than one visits that are the same distance from 56 days after first infusion, data from the earlier/earliest visit will be used.

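### The day-56 visit rule for Overall Response turns on not having withdrawn, so read literally it could score a patient who completes early for HSCT at a post-HSCT visit

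*SAP*

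**What the plan says.** The visit-selection sentence in SAP 6.8.2 (Overall Response) reads: "For subjects that did not withdraw treatment before week 8, observed data from the visit closest to 56 days (8 weeks) after first infusion" are the data to use. If visits tie, "data from the earlier/earliest visit will be used". There is no window around day 56, and nothing limits the choice to visits on treatment or before conditioning.

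SAP 6.3 (Subject Disposition) reports two separate groups: "the number and percentage of subjects who completed the treatment period prior to HSCT and those withdrawn from the treatment will be presented". Protocol 6.5.1.4 also distinguishes completing treatment from discontinuing it.

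Three other places fix the timepoint:

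- The paragraph just before the visit rule in SAP 6.8.2 counts patients "achieving Overall Response at EOT or week 8 (whichever occurs earlier").
- Estimand 2.1 in SAP section 3 says the same.
- SAP Figure 1, with the same labels in protocol Figure 1 and protocol Table 3, marks the week 8 visit as "Primary assessment timepoint if treatment continues" and the EOT visit as "Primary assessment timepoint if treatment stopped before week 8".

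**The concern.** Treatment is planned to run until conditioning for HSCT, which can begin before week 8. In the vocabulary of SAP 6.3, a patient who stops for that reason has completed and has not withdrawn. The day-56 sentence then applies to that patient, and the nearest visit may come after the transplant. The endpoint definition and Figure 1 send the same patient to EOT. Two rules in one plan therefore select different data.

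The day-56 sentence is the operational one. According to the SAP modification history, version 3.0 updated the method to make clear which visit supplies the observation, so a programmer would look there. Nothing nearby stops a post-HSCT visit from being used:

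- The treatment policy strategy is applied regardless of intercurrent events.
- The neighbouring endpoints carry limits that this one lacks. Time to first response is restricted to the period before HSCT, and duration of response ends at EOT.

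At stake is what the response rate measures. The no-cytopenia criterion needs neutrophil and platelet thresholds met with at least 4 days free of G-CSF and transfusion. The adverse events listed in SAP Appendix 1 block Complete and Partial Response. After conditioning, these may reflect the transplant and not emapalumab.

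**Working it through.** **Inputs from the documents**

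- Target day: 8 × 7 = 56, which agrees with the SAP.
- EOT: 3 ± 1 days after the last infusion (protocol 6.5.1.3).
- Pre-conditioning visit: may be combined with EOT if the two are at most 5 days apart (protocol 6.5.1).
- Post-HSCT visits: weeks 1, 2 and 3 and day +30, each ± 2 days, then day +60 and day +100 (protocol 6.5.1 and Table 4).
- Patients: 10 to 18 (SAP section 2).

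**Assumptions, not in the documents**

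- Last infusion on any day from 7 to 52, with EOT exactly 3 days later.
- Pre-conditioning visit 0 or 5 days after EOT.
- HSCT 7, 10 or 14 days after the pre-conditioning visit.

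**One patient.** Last infusion day 28; EOT 28 + 3 = day 31, combined with the pre-conditioning visit; HSCT 31 + 7 = day 38.

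| Visit | Day | Distance from day 56 |
|---|---|---|
| EOT | 31 | 25 |
| Post-HSCT week 1 | 38 + 7 = 45 | 11 |
| Post-HSCT week 2 | 38 + 14 = 52 | 4 |
| Post-HSCT week 3 | 38 + 21 = 59 | 3 |
| Post-HSCT day +30 | 38 + 30 = 68 | 12 |

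The literal rule selects day 59. A ± 2 day shift could make week 2 the nearest, but never EOT. The endpoint definition selects day 31.

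**When the literal rule goes past HSCT.** Let P be the day of the pre-conditioning visit and C the days from it to HSCT. The first post-HSCT visit falls on P + C + 7. Near the boundary it is closer to day 56 than P when (P + C + 7) − 56 < 56 − P, that is, P < (105 − C)/2. The latest EOT that still yields a post-HSCT visit is then:

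| C | Limit on P | Latest EOT, visits combined | Latest EOT, visits 5 days apart |
|---|---|---|---|
| 7 | P < 49 | day 48 | day 43 |
| 10 | P < 47.5 | day 47 | day 42 |
| 14 | P < 45.5 | day 45 | day 40 |

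With EOT after day 48, the literal rule picks the EOT or pre-conditioning visit throughout this range. For example, with last infusion day 49, EOT and pre-conditioning on day 52 and HSCT on day 59, EOT is 4 days from day 56 and the week 1 visit (day 66) is 10 days away.

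Over all 46 × 2 × 3 = 276 assumed schedules, the literal rule selects a post-HSCT visit in 211. The endpoint definition selects EOT in all 276. The 211 is a count of schedules, not a probability.

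**Would the algorithm run on such a visit?** Yes, in the main. Protocol Table 4 schedules vital signs, physical examination, hematology, coagulation, biochemistry and sCD25 at the weekly post-HSCT visits. SAP 6.8.2 falls back on physical examination for spleen size when there is no ultrasound. The program could return a category without flagging anything.

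**Effect on the result.** One responder becoming No Response moves the rate by 1/10 = 10.0 points or 1/18 = 5.6 points. With illustrative counts and Clopper-Pearson 95% limits:

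| Responders | Rate | 95% CI |
|---|---|---|
| 6/10 | 60.0% | 26.2 to 87.8 |
| 5/10 | 50.0% | 18.7 to 81.3 |
| 11/18 | 61.1% | 35.7 to 82.7 |
| 10/18 | 55.6% | 30.8 to 78.5 |

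A move from Complete to Partial Response changes the Overall Response rate by zero. It changes only the category percentages and their intervals, which SAP 6.8.2 also reports.

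**The case against.** The best reply is that the plan already answers the question. The sentence before the rule, Estimand 2.1, both design figures and protocol Table 3 all lead to EOT when treatment stops before week 8, and stopping naturally includes stopping for HSCT. The day-56 sentence then only says which visit stands for week 8 when week 8 applies. SAP section 9 lists changes from the protocol and records no change of timepoint. The argument also leans on one word: the causality definition in protocol 6.5.5.1.3 uses withdrawal of the IMP to mean simply stopping the drug, and on that meaning an early completer falls outside the sentence.

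Much of this stands. A reader might infer that early completers *would* be scored after conditioning; the documents do not support that, because several places point to EOT. A reader might also infer that every affected patient shifts the response rate. That too is unsupported: Overall Response pools three categories, and failing the cytopenia criterion alone rules out only Complete Response. Finally, the 70% of treatment-experienced patients who went on to transplant in the earlier study (protocol 4.1.1.3.2) does not show how many are exposed, since that figure has no week-8 limit.

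The reply does not remove the conflict. The selecting sentence has the wrong condition when set against SAP 6.3, and it does not restrict the visits. The by-patient listings required in SAP 6.8.2 make a misselected visit detectable, but the response algorithm runs only after database lock.

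**Conclusion.** The point holds as a conflict of wording in the operational rule: a patient who completes before week 8 for HSCT *could* be scored after the transplant, contrary to the stated endpoint. On the assumed intervals this requires EOT no later than about day 40 to 48. The cost is at most 10.0 points (n = 10) or 5.6 points (n = 18) per patient, and only where a responder falls to No Response.

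The documents do not give the number of patients likely to reach conditioning before week 8, which could be none, or how often post-HSCT findings would change a category. The endpoint is secondary and descriptive, with no hypothesis test. The sentence should be corrected before programming, but the point does not threaten the study's primary analysis.

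**What to change.** Replace the visit-selection sentence in SAP 6.8.2 with:

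> If the EOT visit occurs before day 56, use the EOT visit, whatever the reason treatment ended, including completion for HSCT. Otherwise use the on-treatment visit closest to day 56, no later than EOT.

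Keep the existing tie rule. Apply the same text to the modified-definition analysis in SAP 6.12, which is tabulated in the same way. Under this wording all 276 assumed schedules are scored at EOT and no post-HSCT visit can be selected. The cost is one replaced sentence and a cross-reference; no data collection changes.
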